Arendse et al[19] reported that 7.5 hours of training over 5 consecutive days was required to learn FF landing, while Dallam et al[20] reported a 1-hour session for 12 weeks was necessary. Diebal et al showed FF landing could be trained in 6 weeks, with training sessions 3 times per week for 45 minutes[8]. An 8-session faded-feedback approach was used by Barrios et al to retrain walkers. This design produced changes in lower extremity biomechanical variables immediately post-intervention as well as at 1-month follow-up [1]. Subjects who receive intermittent feedback have been shown to perform better in the long-term than subjects who receive continuous immediate feedback[21,22]. Removing the feedback is beneficial to motor skill learning because the subjects must rely on internal cues for performing correct motor patterns[23].

Some researchers have suggested that further studies should investigate the effect of gait retraining on injury prevention in runners[8,19]. Changing a runner's gait to reduce the risk of a certain injury, however, may have unintended consequences such as increasing the chance of another kind of injury if other kinematic or spatiotemporal variables are adversely impacted[2,19]. Knowledge of the independent contributions of identified kinematic and spatiotemporal risk factors to impact loading and injury

incidence will allow for targeted modification of these variables so that the risk of negative consequences is limited.

Hypotheses

It is hypothesized that after a 15-week training program, a change in knee flexion at IC will be significant ($p < 0.05$) and will result in decreased impact loading (AVLR) and incidence of RRI.

Outcome Measures

Primary outcome measures:

- 1) Kinetic outcomes: Average vertical loading rate (Body weights [BW] per second) and vertical impact peak (BWs).
- 2) Incidence of RRI (calculated as the number of new injuries reported per 100 runners at risk).

Secondary outcome measures:

Secondary outcome measures will be kinematic and/or spatiotemporal correlates of impact loading and incidence of RRI as guided by the literature and determined in previous studies.

- 1) Knee flexion angle at IC
- 2) Peak knee flexion angle
- 3) Angle of the shank at IC

Other outcome measures:

Other outcome measures will be collected to describe and assess the success of the gait modification intervention. These measures include:

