- 1) Participant compliance: Participant compliance with the gait modification intervention will be measured by the number of training sessions attended at Fortius (to a maximum of 8, converted to a percentage) and the number of home training sessions completed (to a maximum of 22, converted to a percentage). Participants will record their home training sessions in their weekly online questionnaire.
- 2) Adverse events: Adverse events experienced due to the intervention (i.e. increased pain or a new injury) will be recorded in the weekly online questionnaires.
- 3) Fidelity of training sessions: Assessed by calculating the difference (error, in degrees) between the intended target angle and the actual angle produced during the 10 consecutive stance phases at each of the four time points during each training session (first min, 33%, 66%, and last min) and averaged within the session.
- 4) Perceived difficulty in achieving targeted modification: Assessed at each training session using an 11-point numerical rating scale (NRS) (0 = “no difficulty”, 10 = “unable to perform”).
- 5) Pain: Assessed at each training session using an 11-point NRS (0 = “no pain”, 10 = “worst pain imaginable”).
- 6) Rating of Perceived Exertion (RPE): Assessed at each training session using the 15-point Borg RPE scale.

- 7) Anthropometric and functional measurements: These will include BMI, navicular height, hip internal/external rotation range of motion, Q-angle, and weight-bearing ankle dorsiflexion and knee valgus angle.

Methods

The proposed study is a repeated measures design. A sample size calculation for comparing injury incidence is based on our current injury rate (27.9%) in our previous studies. We calculate that we will require a sample size of 30 to achieve a minimum power of 80% ($\alpha = 0.05$). Thirty uninjured female recreational runners will be recruited through advertisements in Vancouver-area running clinics. Participants must be female between the ages of 18 and 60; have been running for at least three months prior to study commencement; and have experience with running on a treadmill. Participants must not have run more than two half marathons previously. Participants will be excluded if they have experienced a lower extremity injury in the prior three months; have undergone hip, knee, or ankle joint surgery; or currently have pain in their lower back or lower extremities while running.

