Eligible participants will first be screened for the biomechanical trait in question (less than 10° of knee flexion at IC). A historical control group from a previous study will be used as a comparison group and a sample that meets the same screening criteria will be matched for age and BMI.

Demographics and a detailed training and injury history will be taken for each subject, which will include information on running experience, previous best times at 5km, 10km, half marathon and marathon distances (if available), and overall number and

type of general musculoskeletal and/or running injuries. Anthropometric and functional measurements (including height, mass, foot length, navicular height, hip internal/external rotation range of motion, Q-angle, and weight-bearing ankle dorsiflexion) will be collected prior to treadmill testing for descriptive purposes and for use as covariates. Participants will wear their regular running shoes.

[figure not shown]

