Pain, RPE, and perceived difficulty in achieving the targeted modification will be measured in all training sessions using an 11-point NRS (pain and perceived difficulty) and the Borg RPE scale. Adverse events (increased pain or a new injury) and participant compliance with the gait intervention will be assessed in the weekly online questionnaire.

All participants will return to the Fortius Biomechanics Lab at the conclusion of the 15-week half-marathon clinic for retesting. A one-month post-test will also be performed to assess for retention. During both sessions (follow-up and retention), the participants will be asked to run naturally and then with the modified pattern. The natural pattern will be collected to determine whether it has changed since baseline.

The verbal instruction during each training session will be given by the principal investigator (a sport physiotherapist with clinical experience in gait retraining). The therapist will not be involved in data collection, but will process the data. To ensure blinding, data will be collected by an independent lab assistant and coded to blind for participant number for later processing and analysis by the principal investigator. This process will ensure that the principal investigator is unaware of which participant they are analyzing until the conclusion of the study.

Demographic, anthropometric, and functional variables will be analyzed for differences between the intervention group and a historical control group from our previous studies at baseline using 2-tailed t-tests for normally distributed continuous variables. Injury incidence (number of new injuries reported per 100 runners at risk) will be compared between groups using paired t-tests. Differences in outcomes pertaining to the feasibility of the intervention (perceived difficulty, exertion, fidelity, compliance) will

be assessed in the intervention group between session 1 and 8 using paired t-tests. The biomechanical and clinical outcomes from the follow-up and one-month post-intervention modified patterns will be compared to the baseline values using ANOVAs for repeated measures. Planned pairwise comparisons between the visits will be conducted. Differences will be considered statistically significant at $p < 0.05$. All statistical analyses will be performed using SPSS version 22.0 (SPSS Inc., Chicago, IL).

References

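### If the screening knee angle also serves as baseline, regression to the mean alone can raise natural knee flexion and be read as carry-over of training; the plan does not say whether the two measurements are separate

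*Combined protocol and SAP*

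**What the plan says.** The screening sentence in the Methods reads: "Eligible participants will first be screened for the biomechanical trait in question (less than 10° of knee flexion at IC"). The plan does not say how or when this screen is measured. The Methods then describe history-taking, anthropometry and a single treadmill protocol: three 15-second trials at a speed set to an RPE of 13, with outcomes averaged over 30 stance phases. No further baseline session is described.

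The screened variable is also an outcome. The Hypotheses expect that "a change in knee flexion at IC will be significant", and "Knee flexion angle at IC" is the first secondary outcome.

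At follow-up and at the one-month retention visit, participants run naturally and then with the modified pattern. For the natural run the plan gives an aim: "The natural pattern will be collected to determine whether it has changed since baseline". It names no test for it. The test of change that it does name covers the instructed runs: follow-up and "one-month post-intervention modified patterns will be compared to the baseline values using ANOVAs for repeated measures".

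A historical control group, selected by the same screen and matched on age and BMI, is used for baseline characteristics and injury incidence. No comparison of change in knee angle with that group is planned.

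**The concern.** A cut-off on a measured value picks out runners who are truly low, and also runners who were measured low that day because of marker placement, the speed they settled on, or ordinary day-to-day variation. When the second kind are measured again, their values move back up, so the group mean rises even if nobody has changed.

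The natural-gait comparison is where this would mislead most. A rise in uninstructed knee flexion after 15 weeks would be taken as evidence that the new pattern had been learned and retained. Regression to the mean pushes in exactly that direction, and no concurrent or historical change in knee angle is planned against which to see it. Averaging 30 stance phases removes stride-to-stride noise within a session, but not the variation between sessions that drives the effect.

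**Working it through.** **What the plan supplies.** The cut-off is 10° (Methods, screening). The group size is 30: "Thirty uninjured female recreational runners will be recruited through advertisements in Vancouver-area running clinics". The significance level is 0.05. That sample size was set for injury incidence, so the plan has no figure for knee-angle change to reproduce.

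**What has to be assumed.** The mean and SD of knee flexion among unscreened runners, and the between-session error. None is in the documents. It is also assumed that the screening value is the baseline value and that there is no true change.

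**Formula.** Let the true angle have mean m and between-runner SD s, and let each session add independent error with SD e. Then:
- total SD: S = √(s² + e²)
- standardised cut-off: c = (10 − m)/S
- expected spurious rise = (e²/S) × φ(c)/Φ(c)
- reliability: ICC = s²/S²

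**Ends of the main range.**
- m = 13, s = 5, e = 1.5: S = √27.25 = 5.220; c = −0.575; φ/Φ = 0.3382/0.2827 = 1.196; rise = (2.25/5.220) × 1.196 = 0.52°. ICC = 25/27.25 = 0.92.
- m = 17, s = 4, e = 2.5: S = √22.25 = 4.717; c = −1.484; φ/Φ = 0.1326/0.0689 = 1.925; rise = (6.25/4.717) × 1.925 = 2.55°. ICC = 16/22.25 = 0.72.

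**Simulated false-positive rate.** Thirty runners selected on a measured angle below 10°, no true change, two-sided paired t-test on natural gait. Repeat runs move the ends by a few percentage points at most.

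| Mean | Between-runner SD | Error SD | Spurious rise | Significant |
|---|---|---|---|---|
| 13-17° | 4-5° | 1.5-2.5° | 0.5-2.6° | 25-98% |
| 13-17° | 4-5° | 1.0° | 0.2-0.5° | 15-48% |
| 10° | 4-5° | 1.0-2.5° | 0.2-1.1° | 8-38% |

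The rises in the last two rows use the same formula. Second row: (1/5.099) × 0.3355/0.2781 = 0.24° and (1/4.123) × 0.0944/0.0448 = 0.51°. Third row, where c = 0 and φ/Φ = 0.798: (1/5.099) × 0.798 = 0.16° and (6.25/4.717) × 0.798 = 1.06°.

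**The same check by reliability.** In these terms the rise is (1 − ICC) × S × φ(c)/Φ(c). With mean 12.5° and total SD 5°, c = −0.5, φ/Φ = 0.3521/0.3085 = 1.141, and 5 × 1.141 = 5.71. The last two columns give the share of no-effect trials that are significant.

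| ICC | Spurious rise | Paired t-test | Three-visit ANOVA |
|---|---|---|---|
| 0.70 | 0.30 × 5.71 = 1.7° | 68% | 71% |
| 0.80 | 0.20 × 5.71 = 1.1° | 51% | 53% |
| 0.90 | 0.10 × 5.71 = 0.6° | 28% | 28% |
| 0.95 | 0.05 × 5.71 = 0.3° | 16% | 15% |

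At ICC 0.98, over means of 10-15° and total SDs of 4-6°, the paired test is significant in about 7-16% of trials.

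**With a fresh baseline.** If baseline is a new recording after the screen, its error is independent of selection. Both measurements then have the same expectation and the spurious rise is 0. The simulated false-positive rate was 4.6-5.8% in every setting run.

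**The case against.** The strongest reply is that the premise is not established. The bias needs one recording to serve as both screen and baseline, and nothing in the documents says so. The text has participants screened first and then describes the full laboratory test, an order that also fits a separate baseline. This stands: a reader might infer that the plan reuses the screening value, but the documents are silent. They are equally silent on any second recording, so the point is conditional but open.

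A reader might also infer that the trial's hypothesis could be declared met by regression alone. The documents do not support that. The named ANOVA covers the modified patterns, run on instruction towards a target above 10°, where a deliberate change may be much larger than the bias. The simulations contain no deliberate change and say nothing about how that test would come out.

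Nor do the documents support extending this to the primary outcomes. Runners are not selected on loading rate or impact peak. Those would be affected only so far as their session-to-session fluctuations move with those of knee angle, and no such figure is given. Injury incidence is compared with controls who passed the same screen.

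It would be wrong, too, to say that the study has no control group. It has one, but not for change in knee angle, and the documents do not say whether those runners were measured twice.

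Finally, the size is assumed. The main range implies reliability of 0.72-0.92. Higher reliability shrinks the problem, as the figures at 0.95 and 0.98 show.

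**Conclusion.** The point holds in conditional form. If the screening value is the baseline, natural knee flexion will rise on retesting without any training effect, and a within-group test of that rise will be significant more often than 5% of the time. The excess is large at reliability of 0.9 or below and modest near 0.98. If baseline is recorded separately, the problem disappears.

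It concerns mainly the natural pattern, which bears on a secondary outcome and has no named test. It concerns the instructed pattern less, and the injury comparison not at all. It merits a change because the plan leaves the premise unsettled, the bias favours the intervention, and the remedy is cheap.

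**What to change.** State that the screening measurement is used for eligibility only. At the Week 1 lab visit, before any feedback or cue, record the same three natural-gait trials and use them as the baseline for all within-group change analyses, including the natural pattern. Keep every screened-in runner whatever the Week 1 value; screening again on it would bring the bias back. Name the test for the natural pattern, and report the agreement between the screening and Week 1 values, with the caveat that the screen restricts the range.

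The cost is a few minutes at an existing visit, where kinematic data are already collected, plus a sentence or two in the plan. The apparent change will be slightly smaller. If a separate baseline is already intended, only the wording is needed.

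If the historical controls were measured twice, comparing change between groups would also work: the false-positive rate was 5.0-5.1% in simulation. Whether they were is not stated.

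A one-sample test of natural knee flexion against 10° is not a substitute, because it answers a different question. At mean 17°, SD 4° and error SD 2.5°, the true mean of those selected is already 17 − (16/4.717) × 1.925 = 10.5°, and the test rejects in about 11% of no-effect trials. At mean 13°, SD 5° and error SD 1.5°, it detects a real 2° shift in about 0.1% of trials, against 99.8% with a fresh baseline.

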Official Title: The Effect of a Gait Modification Training Program on Impact Loading and Running-related Injuries

NCT Number: NCT03302975

The Effect of a Gait Modification Training Program on Impact Loading and Running-related Injuries

Objectives

The purpose of this study is to determine whether a gait modification training program can result in a reduction in impact loading and the incidence of running-related injuries (RRI) among recreational distance runners. Knee angle at initial contact (IC) has been identified in a previous study by the principal investigator (pre-submission stage) as both increasing the average vertical loading rate (AVLR) and the incidence of RRI in the female recreational running population. This variable will be modified to determine the effect on impact loading (AVLR) and incidence of RRI using a repeated measures design.

Background

Numerous studies have shown that individuals can be trained to modify aspects of walking and running[1-18]. Moreover, gait retraining has been shown to be effective in treating overuse injuries in runners[4,7,8,18]. However, since it is unclear what variables independently contribute to the recovery from these injuries and whether these variables can be manipulated prospectively to reduce the risk of injury, optimal prevention and treatment of RRI remains unknown. These studies all included some form of feedback to the subjects, which helped them modify their technique. The feedback methods included verbal instructions and real-time visual[1,3,6,7,9,12,17,18] or auditory information[4,5,8,11,15,16]. Other studies used verbal instructions and videotape reviews[13,14] or an extensive training program[8,19]. Many of these studies have used

overlapping instructions and feedback which make it difficult to infer which factors had a causative effect on changing gait mechanics, muscle activation patterns, and ground reaction forces. Others have used feedback that is difficult to reproduce outside of a lab or clinic environment. Simple cues that produce a specific and intended kinematic or spatiotemporal modification are necessary. Furthermore, these cues need to be consistent and reproducible in multiple training environments in order to be retained as part of the motor program.

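### The plan does not say whether the injury controls are the same runners in whom low knee flexion was found to be an injury risk factor, nor that they are chosen without sight of injury outcomes

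*Combined protocol and SAP*

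**What the plan says.** All references are to the combined protocol and SAP.

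- Objectives gives the reason for the target. Knee angle at initial contact "has been identified in a previous study by the principal investigator (pre-submission stage) as both increasing the average vertical loading rate" and the incidence of running-related injury. The size of that study, the cut-off it used and its effect estimate are not given.
- Methods, screening paragraph: new runners must have less than 10 degrees of knee flexion at initial contact. On the comparator it says: "A historical control group from a previous study will be used as a comparison group and a sample that meets the same screening criteria". Age and BMI are the only matching variables.
- Methods, statistical analysis paragraph, describes the comparator as "a historical control group from our previous studies at baseline", now in the plural.
- Methods, sample size: the calculation is "based on our current injury rate (27.9%) in our previous studies". Earlier injury outcomes are therefore already counted.
- Outcome Measures lists injury incidence as a primary outcome.

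The documents do not say which study supplies the controls or where the 10-degree cut-off came from. They also do not say how many controls there will be, or how one is picked when several runners match. The blinding described in Methods covers data collection and the coding of participants for processing, not control selection.

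**The concern.** A trait that is singled out because its carriers had a high observed injury rate tends to have been helped by chance. If those same carriers then serve as the control group, their rate includes that chance excess. Thirty newly recruited runners with the same trait will not reproduce it, so even an ineffective programme would be expected to show fewer injuries than the controls.

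The excess belongs to the control group's injury count itself. Matching on age and BMI, covariate adjustment or a better test would all leave it in place. It acts in the direction of the study hypothesis.

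A separate gap is that controls are chosen when each candidate's injury outcome is already known, and no rule keeps the choice independent of it.

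**Working it through.** **The plan's own figures.** The documents give no injury rate for historical runners under 10 degrees. The 27.9% is the rate in earlier studies and is not stated to be specific to that subgroup. The sample size of 30 cannot be reproduced, because no target rate, sidedness or control-group size is given. With 30 per group and 27.9% in controls, 80% power (two-sided, no continuity correction) would need an intervention rate of about 2.5%. This point therefore concerns the comparison, not that calculation.

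**Inputs.** From the documents: overall rate 27.9% and 30 new runners. Assumed: discovery cohort N of 60, 100 or 200; fraction f of 30% or 50% with the trait; true relative risk RR of 1.0, 1.5 or 2.0; full overlap of control and discovery cohorts; the trait kept only if it reached z > 1.96 as a risk factor.

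**True rates.** Without the trait, p0 = 0.279 / (f × RR + 1 − f). With it, p1 = RR × p0. For f = 30% and RR = 1.5, p0 = 0.279 / 1.15 = 0.243 and p1 = 0.364.

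**Why selection inflates the rate.** Take N = 100 and f = 30%. The standard error of the observed difference is roughly √[0.279 × 0.721 × (1/30 + 1/70)] = 0.098. Significance then needs an observed gap of about 1.96 × 0.098 = 19 points, while the true gap is 36.4 − 24.3 = 12 points. Any significant result here overstates the truth. With N = 200, f = 50% and RR = 2.0, the threshold is 1.96 × √[0.279 × 0.721 × (1/100 + 1/100)] = 12 points. The true gap is 37.2 − 18.6 = 19 points, so selection matters little.

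**Simulation.** There were 40,000 runs per scenario. Up to 30 controls were drawn from the selected cohort's trait group and compared with 30 new trait carriers, with no intervention effect. The comparison was a two-proportion z test on runners injured, not the plan's paired t-test. Excess in the control rate, in percentage points (f = 30% / f = 50%):

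| N | RR 1.0 | RR 1.5 | RR 2.0 |
|---|---|---|---|
| 60 | 20.1 / 13.4 | 13.8 / 9.1 | 8.9 / 6.4 |
| 100 | 16.0 / 10.1 | 9.5 / 6.0 | 5.0 / 3.4 |
| 200 | 11.2 / 7.5 | 4.8 / 3.1 | 1.3 / 1.0 |

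For N = 100, f = 30% and RR = 1.5, the true rate is 36.4% and the expected control rate is 45.9%. Among 30 controls that is 0.095 × 30, or about 3 injured runners too many.

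The chance of a falsely significant benefit, which is 2.3% to 3.0% without selection, becomes (f = 30% / f = 50%):

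| N | RR 1.0 | RR 1.5 | RR 2.0 |
|---|---|---|---|
| 60 | 24.9% / 15.3% | 11.8% / 8.3% | 6.0% / 5.5% |
| 100 | 20.3% / 12.2% | 7.8% / 5.6% | 4.1% / 3.7% |
| 200 | 12.6% / 7.8% | 4.5% / 4.0% | 2.8% / 2.6% |

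If the control cohort is separate from the discovery cohort, the excess from this mechanism is zero by construction.

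**The case against.** The strongest objection is that overlap is not documented. Objectives credits the finding to one earlier study, while the sample-size and analysis text speak of several. The controls could come from a study that played no part in the finding. This stands: a reader might infer that the control cohort is the discovery cohort and that its rate is therefore likely inflated, but the documents show only that overlap is not excluded.

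The size is also sensitive to the assumptions. Knee angle is said to have raised loading rate as well as injury, so it need not have been picked on injury alone, and nothing says the 10-degree cut-off was derived from injuries. A check with a continuous trait and a real association of 0.4 log-odds per standard deviation (top third with the trait) gave an excess of about 9, 5, 3 and 2 points at cohorts of 60, 100, 150 and 200. At 0.7 log-odds it was about 4, 1.5, 0.4 and 0. This too stands: the no-effect column of the table is an upper end, not a forecast.

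It may also be said that known outcomes are a feature of every historical control group, and that the stated criteria (screen, age, BMI) contain no injury information. That is fair. A reader might infer that controls would be picked for their injuries, but nothing suggests it. The missing selection rule is a gap with no predictable direction, so it does not support a claim of inflation.

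What remains is that no text separates the two data sets or fixes an outcome-blind selection rule, and the planned matching would not remove the bias if the cohorts overlap.

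**Conclusion.** The point holds conditionally. The controls come from the investigators' own earlier work and are restricted to the trait that the principal investigator's earlier study linked to injury. The plan leaves open whether they are the same runners. If they are, the control injury rate carries a chance excess that favours the intervention on a primary outcome.

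Taking high-risk controls is not in itself the flaw, though it might be read that way. If low knee flexion truly raises injury risk, the new runners share that risk because they pass the same screen. Only the chance part of the earlier excess is bias.

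The size cannot be derived from the documents. It is 0 if the cohorts are separate. With overlap and selection by significance, it is about +1 to +14 points for a relative risk of 1.5 to 2.0 and a cohort of 60 to 200, and up to about +20 points if the trait has no real effect. Cohort size, trait fraction and the selection process are all assumptions. The investigators know the answer; a reader of the plan cannot find it.

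**What to change.** In Methods, in the screening and statistical analysis paragraphs:

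1. Name the control study or studies, and state whether they produced the knee-angle finding or the 10-degree cut-off. If other data are held, use controls whose injury outcomes did not contribute to that finding.
2. Include every historical runner who started the training programme and meets the screen. Alternatively, fix a seeded age and BMI matching algorithm and run it on a file from which injury outcomes have been removed. State the size of the eligible pool.
3. If the discovery cohort has to be used, label the injury comparison hypothesis-generating and add a sensitivity comparison with the whole-cohort injury rate (27.9%, if that figure describes the cohort used). Describe it as a conservative bound, because it understates the untreated rate if the trait truly raises risk.

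The cost is protocol wording and re-analysis of data already held, with no new participants and no change to the intervention. The downside is a less favourable control rate and a weaker claim on injury.

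### If more than 30 historical runners qualify as controls, the paired test on injury incidence would leave the surplus unused; variable-ratio matched sets would keep them.

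*Combined protocol and SAP*

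**What the plan says.** Outcome Measures lists the incidence of running-related injury as a primary outcome. Methods makes it the basis of the sample size: "A sample size calculation for comparing injury incidence is based on our current injury rate (27.9%) in our previous studies". The stated result is 30, for at least 80% power at α = 0.05, and "Thirty uninjured female recreational runners will be recruited". All 30 receive the intervention.

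The comparison group is not recruited. It is historical, and "a sample that meets the same screening criteria will be matched for age and BMI". The screen is knee flexion below 10° at initial contact. No matching ratio, caliper or algorithm is given. Nor does the plan give the size of the historical pool, the number who pass the screen, or what happens to qualifying runners who are not matched.

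In the statistical paragraph that closes Methods, injury incidence "will be compared between groups using paired t-tests". Methods also says that anthropometric and functional measurements may serve as covariates, but it describes no adjusted injury analysis.

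**The concern.** The controls' data already exist, so using more of them requires no recruitment. With 30 intervention runners planned, the number of controls is the cheapest way to gain precision on the injury comparison. A paired t-test works on within-pair differences, so a second or third control for the same recruit has no place in it. If the earlier study holds more than 30 qualifying runners, the analysis would leave the rest out. A primary comparison would then have a wider confidence interval and less power than the available data allow. Matching on age and BMI is sensible in itself. The difficulty is the one-control limit that comes with the test.

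**Working it through.** **The plan's own figure.** The 30 cannot be reproduced, because no injury rate under the intervention is stated. Back-solving with the usual two-proportion formula (control rate 27.9%, two-sided 0.05, 80% power):
- 30 per group results exactly only for 27.9% v 0% with continuity correction; without the correction, 0% needs 23 per group.
- 30 v 30 without correction reaches 80% power at an intervention rate of about 2.5%.
- A halving to 13.95% would need 133 per group.

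**Inputs.** From Methods: control rate p₀ = 0.279, n = 30 intervention runners, α = 0.05. The rate is the one observed in the team's previous studies; it is not stated to be the rate among runners below 10°. Assumed:
- two-sided testing (two tails are stated only for the baseline comparisons);
- m = 60 or 90 usable controls, set against the m = 30 that the paired test allows;
- intervention rate p₁ = 5%, or 13.95% (= 27.9%/2);
- independent groups, as an approximation to the matched analysis.

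**Precision when both rates are 27.9%.** SE = √[p₀(1 − p₀)(1/n + 1/m)], with p₀(1 − p₀) = 0.279 × 0.721 = 0.2012.

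| Controls m | 1/30 + 1/m | SE (points) | Relative to m = 30 |
|---|---|---|---|
| 30 | 0.0667 | 11.6 | 1.00 |
| 60 | 0.0500 | 10.0 | 0.87 |
| 90 | 0.0444 | 9.5 | 0.82 |

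**Precision at p₁ = 5%.** SE = √[0.05 × 0.95/30 + 0.2012/m] = 9.1, 7.0 and 6.2 points for m = 30, 60 and 90.

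**Power.** All outcomes of two binomials, (30, p₁) and (m, 0.279), were enumerated. The probabilities of those that the test rejects at two-sided 0.05 were then summed.

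| Intervention rate | Test | m = 30 | m = 60 | m = 90 |
|---|---|---|---|---|
| 5% | pooled z | 72% | 81% | 85% |
| 5% | Fisher exact | 55% | 77% | 83% |
| 13.95% | pooled z | 26% | 31% | 33% |
| 13.95% | Fisher exact | 17% | 28% | 31% |

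The normal-approximation formula gives 67.5%, 77.4% and 82.3% at 5%, and 26.1%, 29.7% and 31.5% at 13.95%. The gain is of the same order.

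The Fisher rows overstate the gain. At p₁ = 5%, Fisher power is 58% with 20 controls and 55% with 30, so 30 v 30 happens to be a low point caused by discreteness. The z-test and SE figures are the safer guide.

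**Limit of the gain.** Because the intervention group stays at 30, even unlimited controls give only about 37% power for a halving (normal approximation).

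**Events.** At 27.9%, 30 controls yield about 8 injuries (0.279 × 30 = 8.4) and 60 about 17 (16.7). At 5%, the 30 recruits yield about 1.5.

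**The case against.** **Nobody may be lost.** A reader might infer that eligible historical runners are being thrown away. The documents do not support that. They give neither the pool nor the number who pass the screen, and if 30 or fewer qualify, the change achieves nothing. This objection stands, and it makes the point conditional.

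**One-to-one is not stated.** The matching sentence could equally describe matching the whole qualifying subset at group level; only the paired test implies pairs. A paired t-test is a doubtful choice for injury incidence anyway, and correcting it would lift the limit. This stands as a reading of intent. But if a higher ratio was intended, the planned test cannot use it, so the two statements still need to be reconciled.

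**More controls are not free.** It is tempting to say that the extra controls cost nothing, or that matching should give way to regression on all of them. Neither is supported. Age/BMI matching is the only control of confounding specified for this non-randomised, non-concurrent comparison. So few injuries support little adjustment, which makes abandoning matching a debatable trade of bias against variance. Variable-ratio sets within a caliper avoid most of that objection. They do not touch bias from non-concurrent controls: the interval narrows around the same possible bias.

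**The favourable case is selective.** A fall from 27.9% to 5% is an 82% relative reduction, and the plan states no effect size. For a halving, the gain is about 5 to 7 points and power stays poor. This stands. Nor is the number of controls the only lever: 30 is the output of a calculation, not a stated recruitment limit.

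**Selection may not be blind.** The team already reports an overall injury rate from its previous studies, and Objectives says that an earlier study linked knee angle to injury. This is a reason to write the selection rule down and apply it without the injury data, not a reason to keep one control per recruit.

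**Conclusion.** The point holds conditionally. As written, the analysis of a primary outcome can use at most 30 historical controls, and any further qualifying runners would go unused. With an assumed 60 to 90 usable controls, the null SE falls by 13% to 18%. Pooled z power rises by 9 to 13 points at an assumed 5% intervention rate, and by about 5 to 7 points for a halving. With 30 or fewer there is no gain.

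These figures assume a 27.9% control rate in the screened subgroup, two-sided testing, independent groups and extra controls that all fall within the caliper. Uneven set sizes would give somewhat less. This is a cheap gain in efficiency. It neither rescues power for a moderate effect nor makes historical controls comparable with concurrent ones.

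**What to change.** In Methods, where the historical group is described:
- Report how many historical runners meet the entry rules and the under-10° screen.
- State an age/BMI caliper and form 1:k sets from every qualifying runner within it, with k allowed to vary.
- Fix the rule in advance and select from a file without injury outcomes.

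In the statistical paragraph, replace the paired t-test on injury incidence with a binary matched-set analysis that accepts unequal numbers, such as Mantel-Haenszel or conditional logistic regression. With so few injuries, keep any further adjustment minimal. State the intervention injury rate behind the 30, so that power can be recalculated at the actual number of controls.

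The cost is a few sentences and a count from existing records, with no new data. The downsides are slightly looser age/BMI balance than with the closest single match, and few events to support adjustment. Bias from non-concurrent controls is unchanged and should be acknowledged as a limitation.
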